### 9.2 POPULATIONS FOR ANALYSES

The safety population will include all treated patients. For safety variables, patients in the safety population will be analyzed by the treatment actually received. The modified intent-to-treat (mITT) population will be comprised of all patients randomized and, have values at randomization, and at least 1 post-randomization value for MGS at a regularly scheduled visit (i.e., Day 14 or Month 1). All patients in the mITT population will be analyzed by the treatment received. This population will be used for the primary and the secondary efficacy analyses.

The method of Last Observation Carried Forward (LOCF) will be used for efficacy on the mITT

population. In these analyses, non-missing values recorded at visit 3 (i.e., Day 14) or later will be used to replace missing data at visits where data are not recorded.

Additional imputation methods will be used for sensitivity analysis and will be outlined in the Statistical Analysis Plan (SAP).

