6 ANALYSIS POPULATIONS

6.1 INTENT TO TREAT POPULATION (ITT)

The intent-to-treat (ITT) population for this study includes all enrolled and randomized patients.

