6.2 MODIFIED INTENT TO TREAT POPULATION (MITT)

The modified intent-to-treat (ITT) population for this study includes all patients randomized and, who have values at randomization, and at least 1 post-randomization value for MGS at a regularly scheduled visit (i.e., Day 14 or Month 1). All patients in the mITT population will be analyzed by the treatment received. This population will be used for the primary and secondary efficacy analyses.

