7.3 METHODS FOR WITHDRAWALS AND MISSING DATA

The method of Last Observation Carried Forward (LOCF) will be used for efficacy on the mITT population. In these analyses, non-missing values recorded at visit 3 (i.e., Day 14) or later will be used to replace missing data at visits where data are not recorded.

If more than 5% of patients are missing data for MGS score or OSDI at 3 months prior to LOCF, then multiple imputation will be used for a sensitivity analysis for these endpoints. Missing MGS score at 3 months (prior to LOCF) will be imputed using a monotone linear regression multiple imputation approach for continuous outcome data. However, assuming the missing data pattern will not be completely monotone at first, then a Markov Chain Monte Carlo (MCMC) imputation will first be carried out using MGS scores at all time points where it is collected (prior to 3 months) to make a monotone missing data pattern. There will be 50 datasets generated in this manner to create 50 datasets with a

	TEMPLATE		
	DOCUMENT #:		TMP-191
	REVISION:		2.0
STATISTICAL ANALYSIS PLAN TEMPLATE	CC #:	836	PAGE 14 OF 25

monotone missing data pattern. For each of these 50 data sets, missing MGS score at 3 months will then be imputed once from a monotone multiple imputation linear regression model with independent variables: age, gender, duration of disease, and TBUT at month 3. Also included will be baseline and post-baseline non-missing MGS scores. The ANCOVA model will then be carried out on each of the resulting 50 complete datasets, with the ANCOVA results being combined across the 50 complete datasets using standard multiple imputation theory to obtain one overall p-value assessing the treatment on reduction in MGS score after accounting for missing data.

The same analysis will be conducted for missing OSDI data at 3 months if more than 5% of subjects are missing this assessment, using baseline and post-baseline non-missing OSDI in the imputation model.

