13 SUMMARY OF CHANGES FROM THE PROTOCOL

The following table provides a list of changes from the protocol to the SAP, and the justification for each change.

Section	Description	Justification
9 Efficacy Analyses	Removed reference to pairwise comparisons between treatment groups.	Throughout the protocol, there is reference to performing pairwise comparisons between treatment groups which is thought to be leftover from the AZ201801 study where there were more than 2 treatment groups. For this study, we will use LSMEANS to compare the two treatment groups, as applicable.

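### SAP 7.3 runs its only missing-data sensitivity analysis when more than 5% of patients lack Month 3 data, with no named denominator, although Protocol 9.2 commits to it without condition

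*SAP*

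**What the plan says.** Protocol 9.2 sets LOCF on mITT as the efficacy method and then states: "Additional imputation methods will be used for sensitivity analysis". It leaves the outline to the SAP and gives no threshold.

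SAP 7.3 keeps the same primary method: "The method of Last Observation Carried Forward (LOCF) will be used for efficacy on the mITT population". Multiple imputation follows only "If more than 5% of patients are missing data for MGS score or OSDI at 3 months prior to LOCF". The rule is repeated for the symptom endpoint: "The same analysis will be conducted for missing OSDI data at 3 months if more than 5% of subjects are missing this assessment". No other missing-data sensitivity analysis is described. The mITT2 repeat in SAP 6.3 is labelled a sensitivity analysis, but it is a subset by baseline severity. SAP 13 declares one change from the protocol: "Removed reference to pairwise comparisons between treatment groups".

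On populations, SAP 6.1 reads "The intent-to-treat (ITT) population for this study includes all enrolled and randomized patients", while SAP 6.2 limits mITT to "all patients randomized and, who have values at randomization, and at least 1 post-randomization value for MGS at a regularly scheduled visit", specified as Day 14 or Month 1. SAP 9.1 and 9.2 evaluate the two primary endpoints in mITT and mITT2 only.

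The imputation covariates in SAP 7.3 are age, gender, duration of disease, Month 3 TBUT and the available MGS scores (OSDI scores for OSDI). Treatment group is not among them. Pooling is described as "ANCOVA results being combined across the 50 complete datasets using standard multiple imputation theory to obtain one overall p-value".

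**The concern.** A commitment made without condition in the protocol became conditional in the SAP, and the list of changes does not record it. Both primary results rest on LOCF in a set defined partly by post-randomisation data, so the sensitivity analysis is the one place where the handling of missing data is tested.

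Two groups can escape it. The first is a carried-forward patient when the missing share stays at or below 5%. The second is anyone who leaves before the first usable gland assessment. On the mITT reading of the rule, such a patient is neither counted as missing nor imputed. Because SAP 7.3 speaks only of patients or subjects, two analysts could apply the rule differently to the same data.

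**Working it through.** **1. The plan's own sample size.** Inputs from SAP 4: MGS SDs 3.35 and 9.48, difference 10.4; OSDI SDs 13.01 and 6.79, difference 15.9; alpha 0.05, two-sided. I used a noncentral t with standard error √((s₁² + s₂²)/n) and Satterthwaite degrees of freedom.
- MGS: 12 per group gives 91.4% power (11 gives 88.4%).
- OSDI: 11 per group gives 91.9% (10 gives 88.8%).

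The stated 12 and 11 reproduce. About 30 are to be randomised 1:1, so about 15 per arm. Neither document gives a dropout rate, so the loss rates in step 4 are assumptions.

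**2. The trigger.** The rule is m/N > 0.05, with m patients missing Month 3 out of N.

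| N | m = 1 | m = 2 | m = 3 |
|---|---|---|---|
| 30 | 3.3%, no | 6.7%, yes | 10.0%, yes |
| 28 | 3.6%, no | 7.1%, yes | 10.7%, yes |
| 24 | 4.2%, no | 8.3%, yes | 12.5%, yes |

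Two missing would escape only with N of 40 or more (2/40 = 5.0%), and three only with 60 or more. At this trial's size exactly one analysed patient can be carried forward unchecked: 1/30 = 3.3% overall, 1/15 = 6.7% of an arm.

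**3. Early leavers.** Suppose 2 of 30 leave before any post-baseline MGS and 1 other misses Month 3.
- mITT denominator: 1/28 = 3.6%, so no imputation.
- All randomised: 3/30 = 10% lack Month 3 data, so imputation runs.

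The unnamed denominator therefore decides the outcome. Ten per cent is an illustration and not a limit: 3 early leavers plus 1 of 27 (3.7%) makes 4/30 = 13.3%.

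**4. How often this could happen.** Let E ~ Binomial(30, early rate) and L ~ Binomial(30 − E, late rate). The event is (E + L)/30 > 0.05 while L/(30 − E) ≤ 0.05.

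| Assumed early / late loss | Probability |
|---|---|
| 5% / 5% | 38% |
| 3% / 7% | 19% |
| 7% / 3% | 60% |
| 5% / 10% | 15% |

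In 16% to 46% of these cases L = 0. No mITT patient then lacks Month 3, and the whole gap comes from the mITT exclusion.

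**5. Treatment in the imputation model.** Take the two early leavers as active-arm patients, vehicle gain 0 and active gain 10.4, with uninformative baseline covariates. A model without treatment imputes both near the mean of the 28 observed patients, 10.4 × 13/28 = 4.83. The active mean becomes (13 × 10.4 + 2 × 4.83)/15 = 9.66. That drop comes from leaving treatment out of the model and says nothing about how the leavers fared.

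**6. Pooling.** The SAP fixes no degrees of freedom. The complete-data ANCOVA with 30 patients has 30 − 4 = 26 for MGS and 30 − 5 = 25 for OSDI. The classical Rubin value is 49/λ² for 50 imputations, where λ is the share of variance due to missing data: 19,600 at λ = 0.05 and 1,225 at λ = 0.20. The Barnard-Rubin value is 19 to 23 over the same range (MGS). A statistic of 2.00 gives p = 0.056 on 26 degrees of freedom and p = 0.046 on the classical value.

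Simulated null trials (30 patients, 50 imputations, 2 to 4 values missing at random) rejected at nominal 5% as follows:
- Treatment in the model: about 5.4% to 6.8% with classical degrees of freedom, mostly near 6%; about 4.1% to 5.6% with Barnard-Rubin.
- Treatment omitted, as the SAP lists it: about 2.4% to 5.3% classical; about 1.8% to 4.0% Barnard-Rubin.

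**The case against.** Protocol 9.2 hands the outline to the SAP, and a threshold could be called part of that outline. This stands for the choice of method. It is weaker for whether any such analysis is done, since the protocol says it will be.

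One unchecked patient in a phase 2b trial of about 30 is a small matter. That stands and limits the size of the point.

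The losses would also be visible. SAP 7.2 tabulates completed assessments for ITT, mITT and mITT2 and terminations by reason, and Protocol 4.2.3, 7.1 and 7.2 ask for exit assessments in early leavers. So the documents do not support an inference that missing data would go unseen. Counts, however, do not show what the losses do to the estimate.

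Three stronger readings are tempting, and none is supported:
- A reader might infer that 10% of patients can be carried forward by LOCF without a check. With 30 analysed, 3 missing triggers the imputation. The 10% arises only by adding early leavers, who have no carried-forward value, and only on the mITT denominator, which SAP 7.3 implies but does not state.
- A reader might infer that the wider imputation would expose an inflated effect: if the two active leavers had gained nothing, the effect over all randomised would be 10.4 × 13/15 = 9.0. That is missing not at random, while the method assumes missing at random. In a simulation of this case, imputation with treatment in the model returned 10.5, the same as mITT.
- A reader might infer that large-sample pooling makes the check easier to pass than the primary analysis. With the covariates the SAP lists, treatment is omitted and the null rejection rates do not show this.

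**Conclusion.** The concern holds in a limited form. The SAP narrows an unconditional protocol commitment, does not declare this, and does not say which patients the 5% refers to. On the mITT reading, one carried-forward patient (3.3% overall, about 6.7% of an arm) can go unchecked. Separately, patients with only baseline data enter no planned primary-endpoint analysis, so the share of randomised patients without Month 3 data can reach 10% or more while the rule reads below 5%. How likely that is (15% to 60% in step 4) depends on assumed loss rates and on the mITT denominator. The pooling issue is secondary: it becomes mildly liberal only once treatment is in the imputation model, as it should be.

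**What to change.** In SAP 7.3:
1. Delete the 5% condition. Run the multiple imputation for MGS and OSDI whenever any randomised patient lacks an observed Month 3 value.
2. Count missingness and impute over the ITT set of SAP 6.1, so that patients with baseline data only are included. The primary analysis stays LOCF on mITT.
3. Add treatment group to the imputation covariates, so that imputed values are not pulled towards no difference.
4. Pool with Barnard-Rubin degrees of freedom, taking complete-data values of 26 (MGS) and 25 (OSDI), adjusted to the actual N.

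If the sponsor prefers to keep a threshold, SAP 7.3 should name its denominator and SAP 13 should list it as a change from Protocol 9.2.

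The cost is a few sentences and a little more analysis, since the imputation program is already planned. One detail needs settling: Month 3 TBUT, a listed covariate, will usually be missing in the same patients and must be imputed with the outcome or left out. The sensitivity estimate may be slightly less precise than the LOCF result.

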9 EFFICACY ANALYSES

9.1 PRIMARY EFFICACY SIGN FOR MGD

The primary sign for MGD is based on change from baseline in meibum gland secretion (MGS) score (0 to 45 scale) at the 3-month follow-up between AZR-MD-001 group versus vehicle group. The primary efficacy sign will be evaluated in the mITT and mITT2 populations and will be analyzed at month 3 using an analysis of covariance (ANCOVA) model with baseline MGS score and duration of disease stratum (< 5 years or ≥ 5 years) as covariates and treatment (AZR-MD-001 ointment/semi-solid drug or vehicle) as factors in the model. The difference between treatment groups will be evaluated using t-tests of the least square means from this model. The two-sided confidence interval (95%) will be provided for the difference between treatments.

The following pseudocode will be used:

```
PROC GENMOD data=xxx;
BY visit;
CLASS treatment (ref = 'AZR-MD-001 VEHICLE') duration;
MODEL chg = treatment base duration;
LSMEANS treatment;
run;
```

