9.2 PRIMARY EFFICACY SYMPTOM FOR MGD

The primary symptom for MGD is based on change from baseline in total OSDI at the 3-month follow-up between AZR-MD-001 group versus vehicle group. The primary efficacy symptom will be evaluated in

	TEMPLATE		
	DOCUMENT #:		TMP-191
	REVISION:		2.0
STATISTICAL ANALYSIS PLAN TEMPLATE	CC #:	836	PAGE 17 OF 25

the mITT and mITT2 populations and will be analyzed at month 3 using an analysis of covariance (ANCOVA) model with baseline OSDI, baseline MGS score stratum (<6 or ≥6) and duration of disease stratum (< 5 years or ≥ 5 years) as covariates and treatment group as factors in the model. The difference between treatment groups will be evaluated using t-tests of the least square means from this model. The two-sided confidence interval (95%) will be provided for the difference between treatments.

The following pseudocode will be used:

```
PROC GENMOD data=xxx;
BY visit;
CLASS treatment (ref = 'AZR-MD-001 VEHICLE') duration baseMGS;
MODEL chg = treatment base duration baseMGS;
LSMEANS treatment;
run;
```

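### SAP 7.3 leaves treatment out of both imputation steps, so its multiple-imputation check pulls a constant or building treatment effect somewhat toward zero (minor)

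*SAP*

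**What the plan says.** SAP 7.3 makes LOCF the main method: "The method of Last Observation Carried Forward (LOCF) will be used for efficacy on the mITT population". If more than 5% of patients lack Month 3 MGS or OSDI before LOCF, multiple imputation is run as a sensitivity analysis in two steps.

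- **Making the pattern monotone.** The MCMC "imputation will first be carried out using MGS scores at all time points where it is collected (prior to 3 months"), so MGS is the only variable named.
- **Imputing Month 3.** This is a "linear regression model with independent variables: age, gender, duration of disease, and TBUT at month 3". The SAP continues: "Also included will be baseline and post-baseline non-missing MGS scores".

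For the symptom endpoint, "The same analysis will be conducted for missing OSDI data at 3 months", with OSDI history in place of MGS history. Neither step names treatment, and imputation by arm is not stated. Protocol 9.2 leaves additional imputation methods to the SAP, and the list of changes in SAP 13 does not address the point.

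The ANCOVA fitted to each of the 50 completed datasets does contain treatment: "MODEL chg = treatment base duration" for MGS (SAP 9.1) and "MODEL chg = treatment base duration baseMGS" for OSDI (SAP 9.2).

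**The concern.** An imputation model should contain every term that the analysis model estimates. Here the term left out is the one being tested. An imputed Month 3 value then carries only the part of the arm difference that passes through the patient's earlier scores and, where available, Month 3 TBUT. The rest is averaged over the two arms.

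This is the only planned missing-data check on LOCF for the two primary endpoints. Repeating the analysis in mITT2 changes the population, not the handling of missing values. If the check has a shrinkage of its own, agreement or disagreement with LOCF is harder to interpret.

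**Working it through.** **The plan's own figures.** SAP 4 gives SDs of 3.35 and 9.48 for MGS (difference 10.4, 12 per group) and 13.01 and 6.79 for OSDI (difference 15.9, 11 per group), for 90% power at 0.05. An unequal-variance t-test gives power 0.884 at 11 and 0.914 at 12 per group for MGS, and 0.888 at 10 and 0.919 at 11 for OSDI. Both stated sizes are reproduced.

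**Inputs**
- MGS: Δ = 10.4, σ² = (3.35² + 9.48²)/2 = 50.55 (σ = 7.11), Δ²/4 = 27.04.
- OSDI: Δ = 15.9, σ² = (13.01² + 6.79²)/2 = 107.68 (σ = 10.38), Δ²/4 = 63.20.
- Missing share p: the trigger is first met at 2/30 = 6.7%. The larger case is 6/30 = 20%.
- Assumed, because the documents do not say: equal correlation ρ between visits of 0.5 to 0.9; share s of the final effect present at Day 14 of 0.3 (slow build) to 1 (constant); values missing completely at random; TBUT left out.

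**Large-sample formula, dropout after Day 14.** Given baseline, the within-arm variance of the Day 14 score is v = σ²(1 − ρ²). Its covariance with Month 3 is c = σ²ρ(1 − ρ). Pooling two equal arms without a treatment term adds the between-arm parts:

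b = (c + sΔ²/4) / (v + s²Δ²/4)

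The arm difference among imputed values is g = b·s·Δ, and the estimate is (1 − p)Δ + p·g. With treatment in the model, g = Δ and the estimate is Δ. If only Month 3 is missing and the effect is constant, replace v by (v + 2c)/3, and b is then the slope on the mean of the three earlier post-baseline scores.

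Worked case (MGS, s = 0.3, ρ = 0.5): b = (12.64 + 8.11)/(37.91 + 2.43) = 0.514 and g = 0.514 × 3.12 = 1.60. With 6 missing: 0.8 × 10.4 + 0.2 × 1.60 = 8.64.

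| Endpoint and pattern | ρ | b | g | 2 of 30 missing | 6 of 30 missing |
|---|---|---|---|---|---|
| MGS, slow build, out after Day 14 | 0.5 | 0.514 | 1.60 | 9.81 | 8.64 |
| MGS, slow build, out after Day 14 | 0.9 | 1.052 | 3.28 | 9.93 | 8.98 |
| MGS, constant, out after Day 14 | 0.5 | 0.611 | 6.35 | 10.13 | 9.59 |
| MGS, constant, out after Day 14 | 0.9 | 0.862 | 8.97 | 10.30 | 10.11 |
| MGS, constant, Month 3 only missing | 0.9 | 0.949 | 9.87 | 10.36 | 10.29 |
| OSDI, slow build, out after Day 14 | 0.5 | 0.531 | 2.53 | 15.01 | 13.23 |
| OSDI, constant, Month 3 only missing | 0.9 | 0.953 | 15.15 | 15.85 | 15.75 |

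Simulation over the same kind of settings gave matching ranges: MGS about 9.8 to 10.4 and 8.6 to 10.3, OSDI about 14.9 to 15.9 and 13.2 to 15.8. With treatment added, the simulated estimates were 10.35 to 10.47 and 15.87 to 15.97. A measured Month 3 TBUT recovered at most about 0.5 MGS units.

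**Bound.** If the earlier effect is not in the opposite direction, g ≥ 0 and the proportional loss cannot exceed p. The MGS floor with 6 missing is 0.8 × 10.4 = 8.32.

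**Comparison with LOCF.** Under the same assumptions LOCF gives (1 − p)Δ + p·s·Δ. With 6 missing after Day 14 and a slow build this is 8.32 + 0.2 × 3.12 = 8.94, close to the 8.64 to 8.98 from imputation as written. With a constant effect LOCF gives 10.4, against 9.59 to 10.11.

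**Waning effect.** With early effects at 1.5 to 2 times the final one, the bias was small and could reverse by about 0.1 unit.

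**The case against.** The case against giving this weight is strong, and most of it stands. The analysis is conditional and secondary. At the trigger the loss is about 0 to 6%, and it works against an efficacy claim. The larger losses need about 20% missing, and the largest also need a slow-building effect. Neither is documented.

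The planning differences may also be generous. Protocol 2.2 reports Month 3 MGS changes in the previous study of 4.9 at 0.5% and 4.5 on vehicle. At a difference of 0.4 the loss with 6 missing is at most 0.2 × 0.4 = 0.08 unit. For OSDI the same section gives −6.9 against 0.0. With s = 0.3 and ρ = 0.5, a difference of 6.9 becomes 6.49 with 2 missing and 5.67 with 6 missing. Those losses of 0.41 and 1.23 are below the 4.5-unit threshold in Protocol 8.1.2.

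Only data missing completely at random were examined, so the sizes do not extend to dropout that depends on arm or outcome.

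Three stronger readings are tempting but unsupported:
- **That the primary result or type I error is compromised.** The LOCF ANCOVA and the gate in SAP 7.5 do not use the imputed data. With no true effect, the omission does not bias the estimate away from zero.
- **That imputed values carry no treatment information, or that the pull is always toward zero.** Earlier scores carry part of the effect, and a waning effect can cancel or slightly reverse the bias.
- **That using Month 3 TBUT as a predictor is a defect of its own.** TBUT, gland evaluation and OSDI share a visit schedule, so a patient with an early-exit TBUT would normally also have early-exit outcomes. In simulation with 6 missing, substituting baseline TBUT barely changed the result (10.30, SE 2.41, against 10.28, SE 2.37).

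None of this answers the core point. The variable lists are explicit, no other section supplies treatment, and following the rule as written gives a shrunken estimate when the effect is constant or building.

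**Conclusion.** The point holds, at minor severity. When a real effect is constant or still building, the SAP 7.3 imputation estimate is pulled somewhat toward zero for both MGS and OSDI. At the planning differences the loss is up to about 6% with 2 of 30 missing and about 17% with 6 of 30. In simulated 30-patient trials the MGS shift was 0.06 to 0.29 standard errors with 2 missing and 0.15 to 0.65 with 6.

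The direction follows from the text and the formula. The sizes rest on assumed attrition, visit correlation and time course, and on values missing completely at random. The consequence is confined to how a conditional sensitivity analysis is read.

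**What to change.** In SAP 7.3, add the treatment variable used in the ANCOVA to both the MCMC step and the monotone regression, for MGS and for OSDI. SAP 6.2 fixes which variable that is: "All patients in the mITT population will be analyzed by the treatment received". Keep the 50 imputations.

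Do not impute separately by arm. The regression has 8 predictors (age, gender, duration, TBUT, baseline and three earlier post-baseline scores) plus an intercept. With 6 missing there are about 12 observed patients per arm, which leaves 12 − 9 = 3 residual degrees of freedom.

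The cost is one or two sentences and one residual degree of freedom: 28 − 10 = 18 instead of 19 with 2 missing, and 24 − 10 = 14 instead of 15 with 6 missing. In simulated 30-patient trials with a true MGS difference of 0 or 0.4, the standard error rose by under 1% with 2 missing and about 4% with 6. At a difference of 10.4 it fell.
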